3.3.2 Follow-up for withdrawn subjects

If participants are withdrawn from the study for any of the reasons noted above prior to randomization, they will be replaced until a total of 45 participants have been randomized to the study. Reasons for withdrawal will be ascertained from subjects who voluntarily withdraw from the study (See End of Trial Form).

4.0 Recruitment Methods

4.1 Identification of subjects

All recruitment for this study will be routed through IRB STUDY00002213 which will also serve as the initial recruitment point of contact.

4.2 Recruitment process

Interested volunteers calling the study center number will first complete the eligibility script and questions for IRB STUDY00002213. If a participant's responses match this study's specified inclusion criteria they will be forwarded to research staff for further screening.

4.3 Recruitment materials

See IRB STUDY00002213.

4.4 Eligibility/screening of subjects

1. **Screener 1 (Phone):** We will consider the screening process and eligibility questions in IRB STUDY00002213 as Screener 1. This process includes a brief phone screening to determine basic eligibility for any of our study center protocols. Then, participants will complete the screening for this study in two additional steps.

2. **Screener 2 (Phone):** A full script and screening questions specific to this study are in the “Consent Forms and Recruitment Materials” section of the IRB application.
3. **Screener 3 (In person, Visit 1):** After a participant has met basic eligibility criteria over the phone, they will be scheduled to come into the study center where they will be consented to the study and further screened for eligibility. See section 7.2 for further details.

5.0 Consent Process and Documentation

5.1 Consent Process

5.1.1 Obtaining Informed Consent

5.1.1.1 Timing and Location of Consent

When participants attend their first in-person visit, they will have the study explained to them in detail, have the opportunity to ask questions, and then will be asked to sign the consent form. Participants will be given a signed copy of the form. This will take place in a private clinic room at the Penn State Clinical Research Center.

5.1.1.2 Coercion or Undue Influence during Consent

Once potential study volunteers are identified, they will be given information about the study and offered the opportunity to participate. The researchers obtaining consent will be instructed to clearly indicate that the participant’s enrolling in the trial is purely voluntary and the researchers will not offer comments about whether they believe the participant should enroll in the study or not. Compensation provided to the participant is modest.

5.1.2 Waiver or alteration of the informed consent requirement

N/A

5.2 Consent Documentation

5.2.1 Written Documentation of Consent

An IRB-approved consent form will be used to document written consent. The participant will be given a copy of the signed consent. The participant’s signed consent form will be uploaded into the participant’s REDCap record.

5.2.2 Waiver of Documentation of Consent (Implied consent, Verbal consent, etc.)

Participants who are interested in the study will be asked to consent to allow the researcher to pre-screen them for the study over the phone by asking all screening questions of all participants (eligible or ineligible). Participants will be asked if this information can be retained so that the study team will know reasons that participants are not eligible for the study.

In addition, participants who are not eligible for the study, or those who begin the phone screener but are not interested in completing it after learning more about the study, will be asked if they would be interested in being contacted for future studies being conducted by our research team. They will be informed that by providing their name and phone number, they will be consenting to allow the study team to contact them in the future.

5.3 Consent – Other Considerations

5.3.1 Non-English Speaking Subjects

N/A

5.3.2 Cognitively Impaired Adults

N/A

5.3.2.2 Capability of Providing Consent

N/A

5.3.2.3 Adults Unable To Consent

N/A

5.3.2.4 Assent of Adults Unable to Consent

N/A

5.3.3 Subjects who are not yet adults (infants, children, teenagers)

N/A

5.3.3.2 Parental Permission

N/A

5.3.3.3 Assent of subjects who are not yet adults

N/A

6.0 HIPAA Research Authorization and/or Waiver or Alteration of Authorization

6.1 Authorization and/or Waiver or Alteration of Authorization for the Uses and Disclosures of PHI

Check all that apply:

- Not applicable, no identifiable protected health information (PHI) is accessed, used or disclosed in this study.** *[Mark all parts of sections 6.2 and 6.3 as not applicable]*
- Authorization will be obtained and documented as part of the consent process.** *[If this is the only box checked, mark sections 6.2 and 6.3 as not applicable]*
- Partial waiver is requested for recruitment purposes only (Check this box if patients' medical records will be accessed to determine eligibility before consent/authorization has been obtained).** *[Complete all parts of sections 6.2 and 6.3]*
- Full waiver is requested for entire research study (e.g., medical record review studies).** *[Complete all parts of sections 6.2 and 6.3]*
- Alteration is requested to waive requirement for written documentation of authorization (verbal authorization will be obtained).** *[Complete all parts of sections 6.2 and 6.3]*

6.2 Waiver or Alteration of Authorization for the Uses and Disclosures of PHI

6.2.1 Access, use or disclosure of PHI representing no more than a minimal risk to the privacy of the individual

6.2.1.1 Plan to protect PHI from improper use or disclosure

Information is included in the “Confidentiality, Privacy and Data Management” section of this protocol.

6.2.1.2 Plan to destroy identifiers or a justification for retaining identifiers

All study data will be retained indefinitely. Paper records will be kept in a safe area in [name] locked research office.

6.2.2 Explanation for why the research could not practicably be conducted without access to and use of PHI

The phone screener (Screener 2) will be used to check eligibility criteria (date of birth), and when participants are screened, their contact information will be used to follow-up about scheduling and for appointment reminders. This requires that we have complete contact (name, phone number) information.

6.2.3 Explanation for why the research could not practicably be conducted without the waiver or alteration of authorization

In order to screen the participants prior to inviting them into the study center, the investigators are conducting a phone screening to determine if the participants are likely to be eligible for the study.

6.3 Waiver or alteration of authorization statements of agreement

Protected health information obtained as part of this research will not be reused or disclosed to any other person or entity, except as required by law, for authorized oversight of the research study, or for other permitted uses and disclosures according to federal regulations.

The research team will collect only information essential to the study and in accord with the ‘Minimum Necessary’ standard (information reasonably necessary to accomplish the objectives of the research) per federal regulations.

Access to the information will be limited, to the greatest extent possible, within the research team. All disclosures or releases of identifiable information granted under this waiver will be accounted for and documented.

7.0 Study Design and Procedures

7.1 Study Design

This is a randomized, double-blind, placebo-controlled, parallel-group study that will occur in three phases over 7 weeks.

Time & Events Table								
	Baseline	Pre-Cessation			Cessation			
Study Week Number	-1	0	1	2	3	4	5	6
Study Visit Number	1	2	Ph #1	3	Ph #2	4	Ph #3	5
Study Day Number	-7	0	7	14	21	28	35	42
MEASURES								
Screener 3	X							
Concomitant medications	X	X	X	X	X	X	X	X
Medical history	X							

NIDA Quick Screen	X						
Cigarette details	X						
Adverse events		X	X	X	X	X	X
Daily cigarette/film diary collection		X	X	X	X	X	X
Demographics	X						
Tobacco Use History	X						
Environmental Tobacco Smoke Questionnaire		X		X		X	X
Cigarette Evaluation Scale		X	X	X	X	X	X
Nicotine dependence		X		X		X	X
Minnesota Withdrawal Scale		X		X		X	X
Questionnaire Smoking Urge		X		X		X	X
Perceived Stress		X		X		X	X
Confidence to quit		X		X		X	X
Study product side effects			X	X	X	X	X
Study product evaluation			X	X	X	X	X
Likelihood of Use Scale				X		X	X
Dose Awareness							X
BIOMEASURES							
Height		X					
Weight		X		X		X	X
Waist/Hip ratio		X					X
Exhaled CO	X	X		X		X	X
Blood pressure & pulse	X	X		X		X	X
Pregnancy test	X			X		X	

7.2 Study Procedures

7.2.1 Baseline Phase – Visit 1 (Consent Visit, Day -7)

At the first study visit, the following procedures will be conducted:

- 7.2.1.1 Prior to informed consent procedures, participants will complete the same screening questions completed over the phone previously (via Screener 2) to confirm eligibility (Screener 3). If participant meets eligibility criteria assessed via Screener 3, they will continue with Visit 1 and be asked to provide informed consent.
- 7.2.1.2 Pregnancy exclusion will be confirmed through a urine test that will be self-administered by the participants when they come to this visit. Participants with confirmed pregnancy will be withdrawn from the study and the End of Trial form will be completed.
- 7.2.1.3 Medical history will be documented to ensure that the participant does not have any conditions that may make them ineligible for the study.
- 7.2.1.4 Concomitant medication history will be recorded to ensure that the participant is not taking any medications that may make them ineligible for the study.
- 7.2.1.5 Details of participants' usual brand cigarettes, including brand name and other characteristics, such as flavor, will be recorded.

- 7.2.1.6** Exhaled CO ≥ 6 ppm will be confirmed. Participants with a CO reading lower than 6 ppm will be withdrawn from the study and the End of Trial form will be completed.
- 7.2.1.7** The NIDA Quick Screen will be administered and participants indicating the use of prescription drugs for non-medical use, illicit drugs, and/or marijuana daily, almost daily, or weekly over the past 3 months will be withdrawn from the study and the End of Trial form will be completed.
- 7.2.1.8** Blood pressure and pulse will be measured. Participants with a blood pressure of systolic >159 mmHg or diastolic >99 mmHg will be withdrawn from the study and the End of Trial form will be completed.
- 7.2.1.9** Participants who meet all eligibility criteria will complete the measures indicated on the Time & Events Table for the baseline visit. Measures will be completed electronically on a participant computer via REDCap. Participants will be given a laptop with access only to the internet, and an individualized REDCap survey will be opened so they can complete direct data entry.
- 7.2.1.10** Participants will be instructed to continue smoking their usual brand of cigarettes for the next week, to avoid using any other tobacco products, and to maintain a daily diary of cigarette use on which they will record the number of cigarettes they smoke each day.
- 7.2.1.11** Participants will be compensated for completing the study visit and procedures.

7.2.2 Pre-Cessation Phase – Visit 2 [1 week after Visit 1] (Day 0 -1/+3 days)

- 7.2.2.1** Adverse events will be documented.
- 7.2.2.2** The cigarette daily diary will be reviewed and recorded by the researcher to confirm that the participant completed their diary, that ≥ 10 cigarettes were smoked on at least 5 out of the last 7 days, and that no quit attempts have been reported. If any of these criteria have not been fulfilled, the participant will be excluded from randomization, and the End of Trial Form will be completed.
- 7.2.2.3** Use of other tobacco products in the past 7 days will be assessed. If the participant has used any other tobacco product in the past 7 days, they will be excluded from randomization, and the End of Trial Form will be completed.
- 7.2.2.4** Concomitant medications will be assessed to confirm participants have not initiated nicotine replacement therapy or cessation medication use since Visit 1. If they have initiated either of these medication categories, they will be excluded from randomization, and the End of Trial Form will be completed.
- 7.2.2.5** Participants who meet all eligibility criteria for randomization will complete the measures and study procedures indicated on the Time & Events Table for the visit.
- 7.2.2.6** Following randomization, subjects will receive their assigned study products. Research staff will explain how to use the nicotine films and provide participants with administration and dosing instructions. Participants will receive a 14-day plus 3-day supply of the assigned film regimen (68 films total). The films will be packaged and numbered so they are taken in a specific, sequential order throughout each day. Participants will be instructed to take one film every 3-4 hours each day for a total of 4 films per day.
- 7.2.2.7** Participants will be asked to return all used (opened/empty) and unused (unopened) study product pouches at their next study visit.
- 7.2.2.8** Participants will be instructed to continue smoking their usual brand of cigarettes ad libitum over the next two weeks and to avoid using any other tobacco products.
- 7.2.2.9** Participants will be instructed to maintain a daily diary of both their cigarette use and nicotine film use. This diary will require that they record the number of cigarettes they smoke each day and the time of day each film was taken.

7.2.2.10 Participants will be compensated for completing the study visit and procedures.

7.2.3 Pre-Cessation Phase – Phone Call #1 (Day 7 ± 3 days)

During this phone contact, daily cigarette/film diary information will be collected, adverse events and changes to concomitant medications will be documented, and participants will be asked to verbally answer the measures indicated in the Time and Events Table during the phone call. Participants' answers will be entered directly into REDCap by the researcher at the time of the call.

7.2.4 Cessation Phase – Visit 3 (Day 14 ± 3 days)

At this in-person visit, the following procedures will be conducted:

- 7.2.4.1** Adverse events will be documented, and any concomitant medication changes will be recorded.
- 7.2.4.2** The daily cigarette/film diary will be collected and recorded by the researcher. Use of other tobacco products in the past 7 days will also be assessed.
- 7.2.4.3** Participants will complete the measures and study procedures indicated in the Time & Events Table.
- 7.2.4.4** All nicotine pouches from the previous weeks (unopened, opened, or empty) will be collected by the researcher.
- 7.2.4.5** Participants will be provided with a new supply of their assigned nicotine films (14-day plus 3-day supply [68 films total]) to use over the next two weeks until their next study visit.
- 7.2.4.6** Participants will be asked to return all used (opened/empty) and unused (unopened) study product pouches at their next study visit.
- 7.2.4.7** Participants will be instructed to cease all cigarette use and to only use their assigned nicotine films beginning the next morning.
- 7.2.4.8** Participants will be provided with the document from the Centers for Disease Control and Prevention titled, "A Report of the Surgeon General: How Tobacco Smoke Causes Disease." Participants will also be given a document with tips to prepare and succeed in a quit attempt.
- 7.2.4.9** Participants will be instructed to continue to maintain a daily diary of their nicotine film use. This diary will require that they record the time of day each film was taken. Participants will be instructed to only record cigarettes smoked on their diary in the event that they experience a slip.
- 7.2.4.10** Participants will be compensated for completing the study visit and procedures.

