1.2 Primary Study Endpoints

The primary endpoints for the study include the percent reduction in the number of cigarettes smoked and the accompanying percent reduction in exhaled carbon monoxide (CO) levels.

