7.2.5 Cessation Phase – Phone Call #2 (Day 21 ± 3 days)

During this phone contact, daily nicotine cigarette/film diary information will be collected, adverse events or changes to concomitant medications will be documented, and participants will be asked to verbally answer the measures indicated in the Time and Events Table during the phone call. Participants' answers will be entered directly into REDCap by the researcher at the time of the call.

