7.4.2 Treatment Regimen

Nicotine films will be administered orally. They are used by placing a film on the tongue, closing the mouth, and pressing the tongue gently to the roof of the mouth. The film will dissolve in the mouth within 5 minutes. Three doses of nicotine film will be used in this study: 0, 2, and 4 mg.

Participants will be randomized to one of three possible treatment regimens:

- 1) **Random nicotine delivery** (a combination of four 0 mg and 4 mg films daily not to exceed three non-consecutive 4 mg films in one day and to maintain an average of 8mg of nicotine per day through 7 days for 6 weeks total)
 - a) Possible weekly random delivery dosing scenarios to maintain an 8 mg/day average through 7 days:
 - a. One 4mg day, five 8mg days, and one 12mg day in any order
 - b. Two 4mg days, three 8mg days, and two 12mg days in any order

Possible Daily Sequences for Random Delivery		
4mg/day	8mg/day	12mg/day
4000	4400	4404
0400	4040	4044
0040	4004	
0004	0440	
	0404	
	0044	

- 2) **Steady state nicotine delivery** (2, 2, 2, 2 mg films daily for 6 weeks total)
- 3) **Placebo delivery** (0, 0, 0, 0 mg films daily for 6 weeks total)

Participants will be directed to take one film every 3-4 hours, in a specified order, for a total of four films consumed daily. In the event that participants miss taking a scheduled film, they will be instructed to skip the film if more than 8 hours has passed since they took their last film. They will be asked to indicate on their daily diary if a film was missed..

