7.4.4 Subject Compliance Monitoring

Participants will be given a paper daily diary to complete on which they will record: 1) the number of cigarettes smoked each day, and 2) the date and time of each nicotine film taken. Participants will be given detailed instructions on how to complete the diary. Questions will be asked at each contact to review participants' logs and to verify their daily conventional cigarette and nicotine film use. Participants will also be asked to self-report their other tobacco use at each visit, including use of products such as electronic cigarettes, cigars, pipes, chew, snus, dip, hookah, and dissolvable tobacco. Exhaled carbon monoxide measurements will be collected throughout the study to verify smoking intensity.

Participants will be asked to return all of their used (empty/opened) and unused (unopened) nicotine film pouches to each study visit following Visit 2. At each of these visits, study staff will document the number of used and unused nicotine film pouches to verify participants' film use and compliance.

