8.3 Statistical methods

Paired sample t-tests (or nonparametric Wilcoxon Rank-Sum tests) will be used to examine changes in the outcome measures (CPD, CO, subjective measures, BP, HR) from baseline.

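### After the quit date the diary asks for cigarettes only on a slip, with no written zero, so an unrecorded smoking day can count as smoke-free in a primary endpoint

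*Combined protocol and SAP*

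**What the plan says.** Section 1.2 names "the percent reduction in the number of cigarettes smoked" as a primary endpoint, alongside percent reduction in exhaled CO.

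Three sections set a daily count. The baseline-week instruction (7.2.1.10) asks for one. So does the pre-cessation instruction (7.2.2.9): "This diary will require that they record the number of cigarettes they smoke each day and the time of day each film was taken". Section 7.4.4 describes the paper diary in general as one "on which they will record: 1) the number of cigarettes smoked each day" and makes no exception for the cessation phase.

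From Visit 3 the instruction differs. Film times are still entered daily, but for cigarettes 7.2.4.9 says: "Participants will be instructed to only record cigarettes smoked on their diary in the event that they experience a slip". Section 7.2.6.8 repeats this at Visit 4. The protocol does not define a slip.

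For films, 7.4.2 does ask for a positive mark when nothing was taken: "They will be asked to indicate on their daily diary if a film was missed".

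On checking, 7.4.4 has staff ask questions at each contact "to verify their daily conventional cigarette and nicotine film use", and Phone Call 2 states that "daily nicotine cigarette/film diary information will be collected". On analysis, 8.3 says only that paired tests "will be used to examine changes in the outcome measures (CPD, CO, subjective measures, BP, HR) from baseline". It gives no scoring rule for a day without a cigarette entry and no averaging window.

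**The concern.** Under the slip rule, a participant who follows instructions and does not smoke leaves the cigarette field empty. A participant who smokes and forgets to write it down leaves the same empty field. The diary alone cannot separate them. Someone who never stops, or who returns fully to smoking, may reasonably not regard ordinary smoking as a slip, so the instruction is least clear for the people with most to record.

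The endpoint is a ratio of follow-up to baseline. Its denominator comes from a diary with an entry for every day, and its numerator from a diary with entries on some days only. Reading a blank as no smoking is the natural consequence of the slip instruction, although no section says so. If blanks are read that way, every error of omission moves the result in the same direction, towards a larger reduction. Counts not captured at the time cannot be rebuilt reliably afterwards.

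**Working it through.** The plan states no figure on this point that could be reproduced, so the check is of the recording rules and of what they imply.

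**Days affected.** Cessation starts the morning after Visit 3 (nominal Day 15), and Visit 5 is Day 42: 42 − 15 + 1 = 28 days.

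**Recall interval at a staff check.** Visit 3 to Phone Call 2 is nominally 21 − 14 = 7 days. If the ±3-day windows count from Day 0, the range is 18 − 17 = 1 day to 24 − 11 = 13 days. Post-quit contacts are Phone Calls 2 and 3 and Visits 4 and 5. The Time & Events Table places post-quit CO at Visits 4 and 5 only.

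**Formula.** Let B be baseline cigarettes per day, C the true post-quit mean and u the share of smoking days neither recorded nor recovered by staff. Score blanks as zero, average over the 28 days, and let unrecovered days carry the participant's average smoking-day count. Then:

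- true reduction R = 1 − C/B
- scored reduction = 1 − (1 − u)C/B
- overstatement = u × C/B = u × (1 − R), which is 0 when u = 0

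**Illustration.** All inputs are assumed, because the documents give neither a mean baseline count nor an under-recording rate. B = 15 and 28 days throughout.

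| Post-quit pattern | C | True reduction | u = 10% | u = 20% | u = 40% |
|---|---|---|---|---|---|
| 3 cigarettes on 4 days | 4×3/28 = 0.429 | 97.1% | 97.4% | 97.7% | 98.3% |
| 10 cigarettes on 14 days | 14×10/28 = 5 | 66.7% | 70.0% | 73.3% | 80.0% |
| 10 cigarettes every day | 10 | 33.3% | 40.0% | 46.7% | 60.0% |

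For the middle row: 1 − 4.5/15 = 70.0%, 1 − 4/15 = 73.3%, 1 − 3/15 = 80.0%. From u = 10% to 40%, the error is 0.3 to 1.1 points in the first row and 6.7 to 26.7 points in the last.

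**The opposite scoring also fails.** If blanks under the slip rule were treated as missing and only days with an entry averaged, the middle-row participant would score 1 − 10/15 = 33.3% against a true 66.7%, even with every slip recorded. A blank-day rule in 8.3 therefore cannot repair the data alone; the diary must carry the zeros.

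**The case against.** The strongest counter-argument is the staff check in 7.4.4. It names daily cigarette use and applies at all four post-quit contacts, nominally a week apart. The analysed record is thus a reviewed log, not an unread sheet. The diary form, its detailed instructions and the data-entry fields are not in the documents, and they may define a slip or have staff enter a zero. No section says blanks will be scored as zero. The 40% rate in a daily smoker would require that share of smoking days to survive weekly review, which nothing supports. If u is the same in every arm, the difference between arms shrinks by the factor (1 − u), which is attenuation and not a spurious effect. Finally, 7.4.4 can be read as a general description that the visit-specific instruction overrides.

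Much of this stands as a limit on size. The check lowers u, the largest figures are extremes, and no false difference between arms is shown. Even so, the check settles a blank by recall, and the protocol does not say that a zero is then entered. Daily film entries reveal an abandoned diary but say nothing about cigarettes. CO at two visits can flag smoking near those visits but cannot supply counts for individual days. At Visit 2 staff must confirm that the diary was completed (7.2.2.2), whereas the post-quit visits say only that it is collected and recorded. If the unseen forms already ask for a zero, the protocol text should agree with them.

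**Conclusion.** The concern holds. As written, the plan collects the two halves of a primary endpoint under different rules, contradicts its own general diary description in 7.4.4, and leaves a blank post-quit day uninterpretable from the diary for 28 nominal days.

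The size is unknown. With blanks scored as zero, the overstatement is u × (100% − true reduction): nil if every slip is recorded or recovered, about 1 point or less in near-abstainers at u up to 40%, and largest in those who relapse. This rests on three assumptions the documents do not settle: blanks score zero, the endpoint averages all 28 days, and unrecovered days resemble the participant's other smoking days. Lighter missed days would give a smaller error and heavier ones a larger error. No bias between arms is claimed. The change should be made because it is cheap and protects primary-endpoint data, not because a wrong conclusion has been demonstrated.

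**What to change.** - In 7.2.4.9 and 7.2.6.8, require a cigarette count for every day through Day 42, with 0 written on smoke-free days. This restores the rule in 7.2.2.9 and removes the conflict with 7.4.4.
- Have staff query every blank day at Phone Calls 2 and 3 and Visits 4 and 5, and enter the answer as a number.
- In 8.3, state that a day still without an entry is missing, not zero, and say over which days the post-quit mean is taken. Setting unresolved days to the participant's baseline rate can serve as a sensitivity analysis; it need not be the primary rule.

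The cost is one sentence in each of two visit sections, a matching diary instruction, a short addition to 8.3, a few seconds of participant effort a day and a brief query at four contacts already planned. A written zero does not prevent deliberate misreporting, but it separates a reported smoke-free day from a day with no report.
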